1.3 Durvalumab

Durvalumab, commercial name IMFINZI®, a PD-L1 inhibitor owned by AstraZeneca, received accelerated approval from FDA for the treatment of patients with locally advanced or metastatic urothelial carcinoma. It comes as 500mg/10mL or 120mg/2.4mL solution in a single-dose vial, and will be further diluted prior to intravenous infusion.

1.4 Clinical Trial

1.4.1 Clinical Data to Date

This clinical trial will be the first trial combining Y90-RE and durvalumab and therefore no previous clinical data of this combination is available.

A similar trial which employs the Y90-RE and PD-1 inhibitor nivolumab is currently in the stage of recruiting/ongoing on clinicaltrials.gov website, but not open yet to the best of our knowledge (NCT03307603). There are other trials employing other checkpoint inhibitors that are showing that they are in development as well (details not available).

1.4.2 Dose Rationale

For each subject, the starting dose of Y90-RE will be personalized based on the lobe and number of metastatic lesions. The actual dose will comply with the FDA-approved prescribing information (Appendix). Each subject will receive a fixed dose of 750mg of durvalumab with at least 2 weeks between doses depending on the dose level assigned to. This will coincide with the Tc99m labelled MAA eligibility mapping and treatment with Y90-RE and every 2 weeks visits with labs post Y90-RE, which is the preferred standard practice at most institutions. As noted in the study schema, there is margin for a few days before or after the planned 2-week cycle to accommodate scheduling issues. The timing and frequency of durvalumab varies on the dose level. Please discuss with the principal investigator and study clinical trial coordinator to know which dose level the patient is assigned to. From a safety perspective since we need to know about the shunting to other organs prior to the Y90-RE, the mapping can be done during the screening or even prior to considerations for this study if already performed within 12 months of intended Y90-RE, it would not need to be repeated unless as per interventional radiology.

Note: The dosing of Y90-RE, dose and administration will be as per FDA approved USPI. Goal is to deliver an ablative radiation dose to the targeted region and trigger a release of neo-antigens in order to augment immunotherapy; all the while minimizing collateral damage by sparing normal liver parenchyma. As noted in the protocol, there are numerous dosing methods in place for Durvalumab.

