3.1 Inclusion Criteria

- 3.1.1 Age \geq 18 years
- 3.1.2 Histological or cytological confirmation of colorectal cancer with metastasis to the liver. Mismatch repair or microsatellite instability status of the tumor needs to be known. Tumors need to be mismatch repair proficient (for mismatch repair deficient tumors immunotherapy is already approved).
- 3.1.3 Patient must have at least 1 liver lesion measurable as defined in [Section 11.0](#).
- 3.1.4 Must have liver metastases and be appropriate for treatment with Y90-RE therapy as determined by the treating medical oncologist and interventional radiologist/oncologist, and nuclear medicine physician(s).

NOTE: the goal of therapy is safety and parenchymal sparing. Typically, since the treatment is personalized, the goal is to have at least 30% liver parenchymal sparing post treatment.

- 3.1.5 Must have a metastatic focus amendable to biopsy. It is permissible to use same or alternative lesion for biopsy for assessment for tumor response and changes in microenvironment (mandatory pre- and post-Y90-RE biopsy).
- 3.1.6 **At least 2 but no more than 3 lines of therapy** allowed in metastatic setting. These include at least treatment with a fluoropyrimidine, oxaliplatin, and/or irinotecan-based

therapy and an anti-EGFR therapy if RAS wild-type (unless deemed intolerant or not suitable by the treating oncologist), with or without an anti-VEGF therapy.

NOTE: adjuvant and/or maintenance chemotherapy does not count as an additional line of therapy. (Patients with more than 3 lines of therapy are at risk for liver disease from prior systemic therapies and would not be reasonable candidates for Y90-RE).

- 3.1.7 At least a 4-week gap between anti-VEGF therapy and the IR Tc-99m labelled MAA eligibility mapping
- 3.1.8 ECOG Performance Status (PS) 0 or 1 ([Appendix I](#)).
- 3.1.9 Negative *serum* pregnancy test done ≤ 7 days prior to registration, for persons of childbearing potential only.

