3.2 Exclusion Criteria

- 3.2.1 Any of the following laboratory abnormalities:
 - Hemoglobin <9.0 g/dL
 - Absolute neutrophil count (ANC) $<1500/\text{mm}^3$
 - Platelet count $<100,000/\text{mm}^3$
 - Total bilirubin $>1.5 \times \text{ULN}$ or $>2.0 \text{ mg/dL}$, whichever is lowest (exception for patients with Gilbert Syndrome, who cannot have a total bilirubin $> 3.0 \text{ mg/dL}$)
 - Alanine aminotransferase (ALT) and Aspartate transaminase (AST) $>2.5 \times \text{ULN}$
 - Serum creatinine $> 1.5 \times \text{ULN}$ or 2.0 mg/dL , whichever is lowest.

OR

 - Calculated creatinine clearance $<30 \text{ ml/min}$ using the Cockcroft-Gault formula below:

Cockcroft-Gault Equation:

$$\text{Creatinine clearance for males} = \frac{(140 - \text{age}) (\text{weight in kg})}{(72) (\text{serum creatinine in mg/dL})}$$

$$\text{Creatinine clearance for females} = \frac{(140 - \text{age}) (\text{weight in kg}) (0.85)}{(72) (\text{serum creatinine in mg/dL})}$$

**NOTE: These can be repeated if outside of range to determine eligibility. Growth factor support not allowed. Transfusion support for low hemoglobin allowed up to 5 days prior to start of treatment.*

3.2.2 Patients with any of the following contraindications to TheraSphere treatment:

- Shunting to the bowel along the gastrointestinal tract
- Lung shunting of $\geq 15\%$
- Estimated dose to lungs ≥ 30 Gy in a single administration
- Cumulative estimated dose to lungs ≥ 50 Gy for multiple administrations
- Liver size ≤ 1.5 L

3.2.3 Prior radiation therapy unless reviewed by the IDE sponsor and approved. This is on a case-by-case basis. Radiation plans should be provided for review.

3.2.4 Persons who are actively breastfeeding a child and unwilling to discontinue.

3.2.5 Co-morbid systemic illnesses, **infections**, or other severe concurrent disease which, in the judgment of the investigator, would make the patient inappropriate for entry into this study or interfere significantly with the proper assessment of safety and toxicity of the prescribed regimens.

3.2.6 Untreated central nervous system (CNS) metastatic disease (including spinal cord and leptomeningeal disease). **NOTE:** Patients with previously treated CNS metastases that are radiographically and neurologically stable for ≥ 6 weeks are permitted.

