4.0 Test Schedule

4.1 Test schedule for metastatic CRC

Tests and procedures	Screening		Active Monitoring Phase					
	Reg	Cycle 1	Cycle 2 (2 nd dose of Durva + Y90-RE)*	Cycle 3	Cycle 4	Cycle 5	End of treatment visit ¹²	Clinical Follow-up ¹³ (every 3 months)
Window	21 days	±5 days	±5 days	±5 days	±5 days	±5 days	±5 days	
History and exam ³ , Wt ⁵ , BP, HR, ECOG PS	X							
Exam, Wt ⁵ , BP, HR, ECOG PS		X	X	X	X	X	X	X
Adverse event assessment	X	X	X	X	X	X	X	X
Concomitant medication review	X	X	X	X	X	X	X	X
Height	X							
IR Consult	X							
Pregnancy test ¹	X		X		X		X	X
Hematology group CBC w/ 5-part differential	X	X	X	X	X	X	X	X
Chemistries ²¹	X	X	X	X	X	X	X	X
Thyroid Function Test TSH, free T4, amylase, lipase, Vitamin D	X		X		X		X	X
Creatinine clearance	X	X	X	X	X	X	X	X
Coagulation PT, PTT, INR	X						X	
Cholesterol, triglycerides	X							
IR Tc-99m labelled MAA eligibility mapping		X ¹⁸						
Tumor measurement ²	X						X	X
ECG ⁶	X		X		X		X	
Urinalysis ⁷	X	X	X	X	X	X	X	X
Administer durvalumab ^{8,R}		X ^{16,17,18,19}	X ^{9,16,17,18,19}	X ¹⁹	X ^{17,18,19}	X ^{17,18,19}		
Administer Y90-RE			X					
Patient Questionnaire Booklets ⁴ (Appendix III)		X	X	X	X	X	X	
Mandatory Research Specimens (see companion Lab Manual) ^{10,R}	X	X ^{14,15,16,17}	X ^{14,15,16,17}	X ¹⁷	X ^{15,16,17}	X ^{15,16,17}	X	
Mandatory Research Tissue specimens (see companion Lab Manual) 11,R	X (Pre- treatment) ₁₈						X (Post- treatment) _{19, 20}	

Cycle = 14 days

1. For women of childbearing potential only. Serum pregnancy test. Must be done \leq 7 days prior to registration.
2. A scan is required at baseline prior to the first dose of durvalumab. The scan does not need to be repeated as long as it is \leq 28 days prior to registration. Preferably we would recommend a CT of the chest and pelvis; and an MRI of the abdomen for assessment of liver metastases. If an MRI cannot be performed, a CT chest, abdomen, and pelvis would be acceptable. Please use same imaging throughout the study.
3. History and exam include prior surgery, cancer-related and other treatment and known positivity for Hepatitis B surface antigen, Hepatitis C virus antibodies, and Human Immunodeficiency Virus antibodies 1 /-2.
4. Patient questionnaire booklets **must** be used; copies are not acceptable for this submission
5. Body weight to be measured within 72 hours prior to durvalumab administration.
6. Single 12-lead ECG after 5 min rest in supine position.

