7. Gross (dipstick) urine examination: Leukocytes, nitrite, pH, protein, glucose, ketone, urobilinogen, bilirubin, blood (hemoglobin and erythrocytes). If abnormalities are detected by dipstick, then a microscopic sediment test should also be performed. If a UTI is suspected, it can be treated.
8. Durvalumab administration over 60 minutes. Following infusion, subjects must be observed for 30 minutes post infusion for potential infusion related reactions. The number of doses administered is per dose level for each patient cohort.
9. The 2nd durvalumab dose can be done \leq 5 days prior to Y90-RE or same day as long as it is before the Y90-RE.
10. Blood biomarkers will be collected in the morning of visit. Kits are required.
11. Tissue specimens must be collected the following timepoints: pre-treatment [screening/prior to cycle 1 of Durvalumab (fresh as well as archived if available)], and post-treatment. Kits are required (banking, clinical as well as real-time send out).
12. Visit will occur 8 weeks after Y90-RE.
13. Clinical follow-up visits will be performed at least every 3 months (or as per standard physician practice) for 2 years.
14. Cohort 1- Durvalumab given at cycle 1 and cycle 2 only
15. Cohort 2- Durvalumab given at cycle 1, 2, and 4
16. Dose escalation cohort- Durvalumab given cycle 1, 2, 4 and 5
17. Dose expansion cohort- Durvalumab given cycle 1, 2, 3, 4, and 5
18. As long as the lesion is amenable to a biopsy and is done, the biopsy can be done on the Tc-99m labelled MAA eligibility mapping day to save patient a visit. Has to be prior to anti-PD1 therapy though. From a safety perspective since we need to know about the shunting to other organs prior to the Y90-RE, the mapping can be done during the screening or even prior to considerations for this study if already performed within 12 months of intended Y90-RE, it would not need to be repeated unless as per interventional radiology. Biopsy still needs to be done as noted.
19. If there is complete response of the lesion in the field of Y90-RE, tissue biopsy of the field would still be done to assess for the immune changes and an alternative tumor lesion can be biopsied for testing of the tumor itself.
20. At the time of progression, patient would be approached for a tissue biopsy and research blood sampling similar to the end of treatment visit.

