6.0 Enrollment Procedures

- 6.1 Call the GI clinical research coordinator/PI for slot reservation.
- 6.2 Correlative research is mandatory in this trial and the subject will automatically be registered to this component (see Sections 3.19d, 3.19e 14.0, 17.31, 17.32, and 17.34). Please contact PI if there are any questions or concerns or exceptions.
- 6.3 Documentation of IRB approval must be on file before an investigator may enroll any patients.
- 6.4 Prior to enrollment, verify the following:
 - IRB approval
 - Patient eligibility
 - Existence of a signed consent form
 - Existence of a signed authorization for use and disclosure of protected health information
- 6.5 Treatment cannot begin prior to screening and must begin \leq 21 days after screening.
- 6.6 Pretreatment tests/procedures (see Section 4.0) must be completed within the guidelines specified on the test schedule.
- 6.7 All required baseline symptoms (see Section 10.3) must be documented and graded.
- 6.8 Treatment on this protocol must commence at University of Iowa Holden Comprehensive Cancer Center institution under the supervision of a medical oncologist.
- 6.9 Case has been discussed or an interventional oncologist has seen the patient and confirms the patient is a suitable candidate for this study.
- 6.10 Study drug is available on site.
- 6.11 Blood draw kit is available on site.

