, where F is the lung shunting fraction measured during the Tc-99m labelled MAA eligibility mapping. Additional eligibility criteria will include the absence of shunting to bowel along the GI tract as well as a lung shunting fraction (F) <15% or estimated lung doses <30 Gy for a single Y90-RE administration and a cumulative total of <50 Gy from multiple administrations. As noted earlier, from a safety perspective since we need to know about the shunting to other organs prior to the Y90-RE, the mapping can be done during the screening or even prior to considerations for this study if already performed within 12 months of intended Y90-RE, it would not need to be repeated unless as per interventional radiology.

16.1.7 **Drug interactions.** External beam radiation is known to interact with immunotherapy, often resulting in heightened immune responses. (Wang et al, 2018, PMID 29556198).

16.1.8 **Radiation observation window.** Due to the long-term side effects of radiation therapy, it is recommended subjects be followed for a minimum of 2 years post-radiation.

16.1.9 **Procurement.** Investigational device will be ordered by the IDE sponsor or delegate. Upon receipt, it will be labelled as per 21CFR§812.5(a) and secured. Subject will be billed for the research device as allowed under 42CFR§405 Subpart B upon approval by the appropriate CMS contractor.

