17.5.3 Overall Response Rate

Overall response rate is defined as the proportion of evaluable patients that have achieved a complete response or partial response using mRECIST evaluation criteria. ORR will be evaluated at 2 months post-Y90RE treatment (\pm 5 business days).

ORR will be analyzed descriptively as a point estimate with a 95% confidence interval.

Results will be reported consistent with RECIST v1.1 (Appendix A.9).

An “evaluable subject” for the purpose of evaluation of the combinatorial therapy is one who receives both Y90-radioembolization and at least 1 dose of durvalumab.

Subjects who do not receive Y90-RE or received only a single incomplete dose of immunotherapy (i.e., allergic reaction), are considered non-evaluable for assessment of efficacy. These subjects would be replaced for the proposed sample size of 18.

All subjects included in the study must be assessed for response to treatment, even if there are major protocol treatment deviations or if they are ineligible.

Each subject will be assigned one of the following categories: 1) complete response (mRECIST), 2) partial response (mRECIST), 3) stable disease (mRECIST), 4) progressive disease (mRECIST), 5) early death from malignant disease, 6) early death from toxicity, 7) early death because of other cause, or 9) unknown (not assessable, insufficient data).

Category 4 (protocol specific definition): includes clinical progression as determined by the principal investigator and confirmed by the independent data and safety monitoring committee (DSMC).

Category 5 (protocol specific definition): death from malignant disease as determined by the principal investigator and confirmed by the independent data and safety monitoring committee (DSMC).

Category 6 (protocol specific definition): death from toxicity as determined by the principal investigator and confirmed by the independent data and safety monitoring committee (DSMC).

Category 7 (protocol specific definition): includes death not meeting categories 5 or 6, or death defined as not otherwise specified.

Category 9 (protocol specific definition): includes subjects who did not receive radioembolization, or who did not receive at least 1 complete infusion of durvalumab, or who did not undergo follow-up imaging (other than for clinical progression, toxicity, or death), or subjects who are lost to follow-up.

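### The schedule places MAA mapping in Cycle 1 with the first durvalumab dose, although the mapping result decides eligibility; at dose levels 1 to 4 a patient can be dosed and then fail mapping

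*Combined protocol and SAP*

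**What the plan says.** Several sections treat the mapping result as a condition of entry. Section 3.2.2 excludes "Patients with any of the following contraindications to TheraSphere treatment" and lists bowel shunting, a lung shunt of 15% or more, and estimated lung doses of 30 Gy or more (single) or 50 Gy or more (cumulative). Section 16.1.6 repeats the shunt and lung-dose limits: "Additional eligibility criteria will include the absence of shunting to bowel along the GI tract". Section 6.4 opens with "Prior to enrollment, verify the following", and patient eligibility is on its list.

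The timing text says something different. In the 4.1 schedule the row "IR Tc-99m labelled MAA eligibility mapping" carries a single mark, in the same column as the first durvalumab mark (Cycle 1); the screening cell is empty. Section 1.4.2 says of durvalumab dosing: "This will coincide with the Tc99m labelled MAA eligibility mapping and treatment with Y90-RE". Footnote 18 to the schedule gives the reason and the allowance together: "we need to know about the shunting to other organs prior to the Y90-RE, the mapping can be done during the screening". It also accepts a map made within 12 months of the intended Y90-RE. Sections 1.4.2 and 16.1.6 use the same permissive wording. Footnote 18 does require something to precede checkpoint therapy, but the subject there is the biopsy.

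Two washouts bear on the order. Section 3.2.11 bars chemotherapy, biologic or hormonal treatment within 14 days of the first durvalumab dose. Section 3.1.7 requires "At least a 4-week gap between anti-VEGF therapy and the IR Tc-99m labelled MAA eligibility mapping".

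On consequences, Section 17.5.3 begins "Subjects who do not receive Y90-RE or received only a single incomplete dose of immunotherapy" and goes on to class such subjects as non-evaluable for efficacy and to be replaced.

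**The concern.** Eligibility that depends on a test cannot be verified before enrollment if the test is scheduled with the first treatment. Nothing suggests a deliberate plan to dose first and map later; the sections simply disagree, and staff working from the schedule would follow the one that dates the procedure.

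The cost falls on the patient first. All participants must be mismatch-repair proficient, and Section 1.1 reports 0 of 18 responses to anti-PD-1 blockade in microsatellite-stable disease. Durvalumab without Y90-RE therefore offers such a patient little, while the immune-related risks remain. The trial also loses information: a patient without Y90-RE drops out of the efficacy set and contributes nothing to the 8-week DLT observation, which 7.4.2 counts from Y90-RE. With one patient per level in the accelerated phase, each such loss delays that level.

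**Working it through.** The plan states no figure on this point, so the check has three parts: order of events, washout arithmetic, and an illustration of size.

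**1. Order of events by dose level** (Table 1 in 1.4.6; 7.1.2)

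- Levels 1 to 4: durvalumab at Week -2 and Week 0, with Y90-RE two weeks after the first dose. Mapping marked in Cycle 1 satisfies the before-Y90-RE deadline but need not precede dose 1.
- Levels -1 and -2: durvalumab only after Y90-RE. The problem cannot arise.

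**2. Washouts.** Count days from the last anti-VEGF dose.

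- Earliest durvalumab under 3.2.11: day 14.
- Earliest mapping under 3.1.7: day 28.
- Gap: 28 − 14 = 14 days.

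A patient who starts durvalumab on days 14 to 27 without a usable earlier map can be mapped only after dose 1. For a day-14 start, planned Y90-RE falls on day 14 + 14 = 28, the first day on which mapping is allowed.

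**3. Size.** The documents give neither a mapping-failure rate nor the share of patients mapped late, so both are assumed. Let f be the failure rate, s the share of patients starting durvalumab whose mapping is still to come, and q = f × s. The target is 18 evaluable patients, from 1.4.6 and 17.3.

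- Expected number dosed and then failing before 18 evaluable: 18q/(1 − q)
- Probability of at least one: 1 − (1 − q)^18

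| s | f | q | Expected number | P(at least one) |
|---|---|---|---|---|
| 1.0 | 2% | 0.02 | 18 × 0.02/0.98 = 0.37 | 1 − 0.98^18 = 0.305 |
| 1.0 | 15% | 0.15 | 18 × 0.15/0.85 = 3.18 | 1 − 0.85^18 = 0.946 |
| 0.5 | 2% | 0.01 | 18 × 0.01/0.99 = 0.18 | 1 − 0.99^18 = 0.165 |
| 0.5 | 15% | 0.075 | 18 × 0.075/0.925 = 1.46 | 1 − 0.925^18 = 0.754 |
| 0 | any | 0 | 0 | 0 |

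The rows with s = 1.0 are an upper bound.

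**The case against.** The best defence is that the binding rules already settle the matter. If 3.2.2 can be assessed only by mapping and 6.4 requires eligibility before enrollment, mapping must come first; likewise, where a 14-day and a 28-day minimum both apply, the longer one governs. On that reading the dose-then-fail path is a breach of 6.4, and 13.9 classes such a patient as ineligible. This is a sensible reading, and probably what was intended. It does not remove the problem, because it contradicts the Cycle 1 mark in 4.1, and 6.6 tells staff to complete pretreatment tests according to that schedule. No sentence requires the mapping result before the first durvalumab dose.

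Other points have some force:

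- The column is read from an extracted table. The mapping mark does align with the first durvalumab mark and sits one column before the Y90-RE mark, and 1.4.2 independently pairs mapping with dosing.
- When biopsy and mapping share a day, as footnote 18 permits, mapping does fall before durvalumab. But sharing is optional, and a same-day map does not oblige anyone to act on the result before dosing.
- Section 13.8 replaces patients who do not complete the first cycle before Y-90 for reasons other than toxicity, and 1.4.6 allows for 10% loss. These protect the patient count; they do not spare the patient the dose.
- The 0 of 18 figure is for anti-PD-1 blockade, and durvalumab is an anti-PD-L1 agent. It supports low expected benefit but does not measure it.
- The size rests on assumed inputs and can be zero. That is correct and limits how much weight the probabilities can bear.

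**Conclusion.** The protocol contradicts itself on when an eligibility-defining test is done. As written, it permits durvalumab at levels 1 to 4 for patients who may then prove excluded under 3.2.2. The conflict rests on the text alone and needs no assumed rate.

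The number affected is unknown. With an assumed failure rate of 2% to 15%, it lies between none, if mapping always comes first in practice, and 0.4 to 3.2 patients with a 30% to 95% chance of at least one, if it never does. It should be corrected because the exposure is avoidable and the correction is cheap. It does not affect the stated sample size or the dose levels.

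**What to change.** - In 4.1, move the mapping mark from Cycle 1 to Screening, keeping the 12-month allowance for an earlier map.
- In 1.4.2, footnote 18 and 16.1.6, state that the mapping result must be assessed against 3.2.2 and found acceptable before enrollment and before the first durvalumab dose.
- State that a patient within 4 weeks of anti-VEGF therapy and without a usable earlier map waits for mapping before dose 1.

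The cost is possibly one extra visit, which the pre-treatment biopsy can already share, and a first durvalumab dose up to about 14 days later for patients recently on anti-VEGF therapy. No new procedure is needed.
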